## 7. Rationale and Background

### 7.1 Diseases and Therapeutic Area

Migraine is a neurological disorder characterized by recurrent headache attacks of moderate to severe pain. Migraines affect up to 18% of the female population and 6% of the male population; the prevalence peaks in middle life (30 to 49 years) (7.9%-9.0% in men and 25.5%-28.1% in women) and is lower in children/adolescents and those older than age 60 (Lipton et al, 2007).

Treatment for migraine includes medications for acute migraine as well as preventive medications. Acute treatments that are commonly used for migraine attacks include triptans, ergots, nonsteroidal anti-inflammatory drugs (NSAIDs), acetaminophen, and antiemetic agents (Charles 2017). The most commonly used therapies for migraine prevention include tricyclic antidepressants, beta-blockers, anticonvulsants (eg, topiramate and divalproex sodium), and botulinum toxin (Charles 2017).

Migraine often improves during pregnancy; however, this varies depending on whether women have migraine with aura. For patients who have migraine without aura, approximately 47% of women will have improvement or remission of migraine in the first trimester, increasing to 83% in the second trimester, and 87% in the third trimester (Sances et al, 2003). Migraine with aura is less likely to improve during pregnancy (Robbins 2018).

Up to 70% of pregnant women with migraine require a behavioral or a pharmacologic intervention (Contag et al, 2009). Although nonpharmacologic therapies are recommended for migraine management during pregnancy, acute medications used to treat migraine include acetaminophen and metoclopramide; however, narcotics, NSAIDs (depending on the trimester) and triptans may also be used (Robbins 2018). Triptans

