are classified as an FDA category C drug. Data from a prospective pregnancy registry observed birth defects in 4.2% (95% confidence interval (CI) 2.6%-6.5%) of infants born to women using sumatriptan during pregnancy (Ephross and Sinclair 2014), which is consistent with general population birth defect rates. Preventive medications that may be used during pregnancy include memantine and beta blockers, such as propranolol (Robbins 2018). Beta-blockers are generally thought to be safe and are commonly used to treat hypertension in pregnant women; however, they may be associated with intrauterine growth restriction (Robbins 2018). Topiramate and valproic acid should be avoided during pregnancy due to their teratogenic effects (Robbins 2018; Hernandez-Diaz et al, 2012).

Erenumab-aooe is a human monoclonal antibody (mAb) that inhibits the receptor for calcitonin gene related peptide (CGRP) and is indicated for the preventive treatment of migraine. Although clinical trials have demonstrated erenumab has a favorable risk benefit profile, there are no adequate and well-controlled studies on the use of erenumab-aooe in pregnant women. In animal reproduction studies, there were no effects on pregnancy or neonatal/infant development when monkeys were administered erenumab-aooe SC from organogenesis through parturition at exposures up to 16-fold the exposure at the maximum recommended human dose of 140 mg monthly.

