## **8. Research Question and Objectives**

### **8.1 Primary**

The primary objective is to estimate and compare the proportion of live-born infants with major congenital malformations among (1) women with migraine directly exposed to erenumab-aooe prior to and during pregnancy, (2) women with migraine exposed to other preventive migraine medications prior to or during pregnancy (comparator group A), and (3) women with migraine not exposed to erenumab-aooe or other preventive migraine medications prior to or during pregnancy (comparator group B). Comparative analyses will be undertaken if there is sufficient sample size and adequate distribution of covariates to adjust for confounding.

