## 9.2.2 Subject/Patient/Healthcare Professional Eligibility

### 9.2.2.1 Inclusion Criteria

Two cohorts of patients will be followed for outcomes:

- 1) Pregnant women with migraine
- 2) Live-born infants of pregnant women with migraine

Inclusion criteria for the cohort of pregnant women with migraine are as follows:

- 1) Women who are pregnant and ages 16-44 years of age at estimated LMP date. Pregnancy will be defined using combinations of ICD-10-CM diagnosis codes and CPT procedure codes, which includes having evidence of at least one of the following pregnancy outcomes: spontaneous abortion, stillbirth, live birth, therapeutic abortion, or ectopic pregnancy.
- 2) Have evidence of migraine during the one year prior to the LMP date or during pregnancy, where migraine is defined using combinations of ICD-10 diagnosis codes for migraine and/or NDC or HCPCS codes for acute migraine medication use (eg, triptans or ergots). Patients will be included if they meet at least one of the following criteria:
  - a. 1 migraine diagnosis claim from a "non-emergency" inpatient visit
  - b. 1 migraine diagnosis claim from an outpatient visit associated with a neurologist (variable STDPROV 260 in MarketScan CCE)
  - c. 1 migraine diagnosis claim from an emergency room visit
  - d. 1 outpatient migraine diagnosis claim **PLUS** 1 acute migraine drug (triptan or ergot-derivative) prescription claim within 180 days of each other
  - e. 2 outpatient migraine diagnosis claims between 7 and 180 days apart
  - f. 2 acute migraine drug (triptan or ergot-derivative) prescription claims between 7 and 180 days

Have complete medical and pharmacy benefits coverage for the twelve months prior to the LMP date through a commercial health plan.

- 3) Have continuous enrollment in the health plan from 365 days prior to the estimated date of conception through the end of pregnancy

Inclusion criteria for the cohort of live-born infants of pregnant women with migraine are as follows:

- 1) Live-born infants (based on a live delivery record) from the cohort of pregnant women with migraine. In the HIRD, the subscriber ID is unique for all family members, and infants with birth dates or enrollment records within 30 days of delivery will be matched. Mother-child linkage in the Marketscan CCE database will be determined using the following criteria:
  - a. Mother's ID (minus last 2 digits) Infant's ID (minus last 2 digits)

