  - b. Mother's earliest delivery related claims date (year) from mother's claims records Infant birth year (from infant enrollment records). For mothers with delivery-related claims in December, infants with records in January of the following year will be included.
  - c. Infant's first enrollment date is not more than 180 days after mother's delivery related claims
- 2) Infants must be continuously enrolled for at least 90 days following birth which allows for the assessment of most major congenital birth defects

For comparator cohort A, we will include women who are exposed to other preventive medications during pregnancy as well as before LMP. When considering exposure to other preventive migraine medications before LMP, women will be included if exposure to these substances occurs within five of their half-lives prior to LMP.

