#### **9.2.4 Baseline Period**

The baseline period to assess relevant covariates, such as demographics, comorbidities, and concomitant medications, will be the 365 days prior to the LMP date. To evaluate history of obstetric outcomes (eg, prior pregnancies, multiple gestation, outcomes of prior pregnancies including spontaneous abortions), we will use all available data prior to the index date.

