### **9.3 Variables**

#### **9.3.1 Exposure Assessment**

Pregnant women who have pharmacy claims for erenumab-aooe (identified using NDC codes) in the 112 days prior to the LMP date (to allow for the half-life of erenumab) or during the pregnancy will be considered exposed to erenumab-aooe.

Exposure to erenumab-aooe will be categorized by dose (70 mg versus 140 mg), by length of exposure, and by timing in relation to trimester of pregnancy: before the last menstrual period (LMP, in the 112 days prior to the EDC, this is the exposure window of interest for major malformations), during the first trimester (from the LMP to 90 days after the LMP), during the second trimester (from day 91 after the LMP to day 180 after the LMP), and during the third trimester (from day 181 after the LMP to the end of pregnancy) (see [Section 9.3.1.1](#) for definitions of LMP).

For the comparator cohorts, comparator group A will include pregnant women with migraine who do not have pharmacy claims for erenumab-aooe in the 112 days prior to the LMP but do have evidence of the use of other preventive migraine medications. Comparator group B will include pregnant women with migraine who do not have pharmacy claims for erenumab-aooe or other anti-CGRP medications 112 days prior to the LMP date or during pregnancy

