### 9.3.3 Covariate Assessment

Study cohorts will be described according to baseline covariates. Demographic attributes will be determined on the cohort entry date while others will be assessed during the baseline period, unless otherwise specified. All covariate information will be ascertained through inpatient and/or outpatient claims for diagnoses and procedures, and through pharmacy claims utilizing ICD-10 CM for diagnoses; ICD-10 PCS, CPT, or HCPCS codes for procedures; and GPI or NDC codes for dispensings. Additional details will be provided in the Statistical Analysis Plan (SAP) and the Medical Record Plan (MRP).

Covariates to be assessed include the following:

- Maternal age at estimated LMP (in years)

- Maternal race, if available

- Calendar year at estimated LMP

- Geographic region of health plan

- Migraine characteristics (eg, migraine with aura, chronic migraine)

- Comorbid conditions at baseline (eg, chronic hypertension, hyperlipidemia, diabetes, polycystic ovarian syndrome, hypothyroidism, hyperthyroidism, depression, anxiety, epilepsy), identified through ICD-10-CM diagnosis codes

- Medications in the baseline period (eg, acute and preventive migraine treatments, other treatments not for migraine, suspected teratogenic medications), identified through NDC codes or HCPCS codes

- Adverse events during pregnancy (eg, pre-eclampsia, gestational diabetes), identified through ICD-10-CM diagnosis codes

- Concomitant medications with claims after or a days supply that overlaps the LMP date and by trimester during the pregnancy (eg, acute migraine treatments, other treatments not for migraine, suspected teratogenic medications), identified through NDC codes or HCPCS codes

- History of obstetric outcomes (eg, prior pregnancies, multiple gestation, outcomes of prior pregnancies including spontaneous abortions) using all available history

- Use of prenatal testing

- Resource utilization (eg, number of prenatal visits, types of providers visited, emergency department visits)

- Body mass index, if available

- Alcohol, tobacco, and substance abuse, if available

Exposure to infections during pregnancy, if available  
 Previous history of congenital malformations, if available

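### Comparator A has no condition on why or when the preventive drug was started, so women treated for hypertension arising in pregnancy can enter it and bias the small-for-gestational-age comparison in erenumab's favour

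*Protocol*

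**What the plan says.** The objectives (Protocol 8.1, and likewise the summary table, the abstract and 8.2) describe the active comparator as "women with migraine exposed to other preventive migraine medications prior to or during pregnancy (comparator group A"). The eligibility text in 9.2.2.1 reads: "For comparator cohort A, we will include women who are exposed to other preventive medications during pregnancy as well as before LMP". It adds that use before LMP counts when it falls within five half-lives of the drug. Section 9.3.1 asks that women in A have no erenumab claim in the 112 days before LMP, "but do have evidence of the use of other preventive migraine medications".

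Every cohort member must "Have evidence of migraine during the one year prior to the LMP date or during pregnancy" (9.2.2.1), but nothing ties the preventive claim itself to migraine.

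On the drugs, 7.1 says: "The most commonly used therapies for migraine prevention include tricyclic antidepressants, beta-blockers, anticonvulsants". It then says of beta-blockers that they are "commonly used to treat hypertension in pregnant women; however, they may be associated with intrauterine growth restriction".

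On adjustment, the baseline period for covariates "will be the 365 days prior to the LMP date" (9.2.4). The hypertension item in 9.3.3 is among "Comorbid conditions at baseline (eg, chronic hypertension, hyperlipidemia, diabetes". Section 9.6.2.4.1 builds the weights from measured baseline confounders, yet points to the whole covariate list of 9.3.3, which includes pre-eclampsia as an event during pregnancy.

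**The concern.** A is meant to hold women treated for migraine prevention. As defined, it holds women with migraine who used a drug of a preventive class, whatever the reason. Section 7.1 itself gives another common reason for one of those classes: hypertension in pregnancy.

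The entry route is one-sided. Erenumab is described in 7.1 as indicated for migraine prevention, so new hypertension does not bring a woman into the exposed cohort, whereas it can bring her into A. Women on erenumab who develop hypertension remain at their natural frequency, while A is enriched.

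Baseline weighting cannot undo this, because the condition that triggers entry arises after the baseline window closes. Putting pre-eclampsia into the weights would not be a clean repair either, since it is a post-baseline event.

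At stake is the SGA contrast with A. If A's SGA risk is raised by women who are not there for migraine prevention, a real excess with erenumab can be understated.

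**Working it through.** **What the protocol supplies.** It gives no base risk, sample size or power for SGA, and no figure for beta-blocker use for hypertension. Table 2 covers malformations only. Its entry of 425 exposed live births for a relative risk of 2.00 is reproduced as 428 (6% v 3%, 1:4, 80% power, pooled two-proportion test, two-sided 5% assumed), but it contains no input for this question.

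**Does such a woman qualify?** With the objectives' wording (before or during pregnancy), first use in pregnancy is enough. If 9.2.2.1 were read as requiring use in both periods, new starters would be excluded. The two places do not say the same thing.

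**Do the planned analyses deal with it?** The exposure-timing analyses in 9.6.2.5.3 vary erenumab timing only. The quantitative bias analyses there are generic. No analysis varies A's start time or indication.

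**Illustration of size.** All inputs are assumptions:

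- base SGA risk without new hypertension: 10%, chosen because SGA is defined by the 10th percentile;
- h0, background share with new hypertension: 10%;
- R, SGA risk ratio for new hypertension: 1.5 to 3;
- f, share of A that entered through a drug given for new hypertension: 10% to 50%.

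Formulas, with no erenumab effect:

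- risk in erenumab women = base × [1 + h0(R − 1)]
- risk in A = base × [1 + (f + (1 − f)h0)(R − 1)]

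For R = 2:

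- erenumab: 0.10 × (1 + 0.10) = 0.110
- A at f = 10%: 0.10 × (1 + 0.10 + 0.90 × 0.10) = 0.119; ratio 0.110/0.119 = 0.92
- A at f = 25%: 0.10 × (1 + 0.25 + 0.75 × 0.10) = 0.1325; ratio 0.110/0.1325 = 0.83

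| Apparent risk ratio, no true effect | f = 10% | f = 25% | f = 50% |
|---|---|---|---|
| R = 1.5 | 0.96 | 0.90 | 0.82 |
| R = 2 | 0.92 | 0.83 | 0.71 |
| R = 3 | 0.87 | 0.73 | 0.57 |

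At R = 2 and f = 25%, a true risk ratio of 1.5 appears as 1.5 × 0.83 = 1.25, and a true 2.0 as 1.66. The protocol's measure is the odds ratio. On that scale the null value at R = 2, f = 25% is (0.110/0.890)/(0.1325/0.8675) = 0.81.

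The direction for SGA does not depend on the particular values: f + (1 − f)h0 exceeds h0 whenever f > 0 and h0 < 1, so the ratio is below 1 for every R > 1. At f = 0 it is 1.00.

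**Could f be appreciable?** Section 9.5 puts preventive use during pregnancy at 0.9% of about 7,000 pregnancies a year in MarketScan: 7,000 × 0.009 = 63. If a further 0.1% of pregnancies (7 a year, assumed) carried a listed beta-blocker for new hypertension, they would be 7/70 = 10% of in-pregnancy users; at 0.5% the share is 0.5/1.4 = 36%. This holds only if the 0.9% does not already count them, and women entering A through use before LMP would lower the share.

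**The case against.** The strongest reply is that the route depends on an operational drug list that is not shown. Section 7.1 is background, and the only beta-blocker it names is propranolol. If the list leaves out the beta-blockers used for hypertension in pregnancy, few such women enter. This stands, and it is why the point is conditional.

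Second, the growth-restriction remark in 7.1 concerns beta-blockers themselves. A comparator drug's own effect is part of an active-comparator contrast, not bias, and limiting A to users before LMP would not remove it. This also stands. The bias described here rests on the assumption R > 1 for new hypertension, which the documents do not quantify.

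Third, the plan has partial safeguards: incident conditions in pregnancy are summarised (9.6.1.1, 9.6.2.3.2), subgroups by concomitant medication are possible (9.6.2.5.1), and quantitative bias analysis is foreseen. These could reveal an imbalance but do not correct it.

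Some stronger readings are tempting and are not supported:

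- *That A's stillbirth risk is raised too.* The documents link neither hypertension nor beta-blockers to stillbirth. A woman entering by a late fill must still be pregnant at that fill. With Table 1's method 2 median of 26.0 weeks for stillbirths, a woman entering after 26 weeks has about half of the stillbirth risk left, so R would have to exceed about 2 before A's risk rose. The sign is open.
- *That the primary malformation result is affected.* Nothing in the documents shows this.
- *That a loss of power can be computed.* One might take 63,000 × 0.9% = 567 as the size of A and set it against the exposed infants (1,400–1,500 × 62% × 77% = 668–716). The first counts pregnancies and the second linked infants. Moreover, 567 is not the size of A, which also admits users before LMP. No power figure is given here for that reason.

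**Conclusion.** The point holds in a limited form. The definition of A lets in women whose preventive-class drug was first given for hypertension arising in pregnancy, if the drug list covers it, and baseline weighting cannot remove the resulting difference. For SGA against A, the bias runs in erenumab's favour whenever such women are present and new hypertension raises SGA risk. Its size cannot be determined from the documents. At R = 2 with 10% background hypertension, the apparent null risk ratio is 0.92 at a 10% share and 0.83 at 25%, and across the assumed grid it runs from 0.96 to 0.57.

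A reader might infer that the study will make erenumab look safer. The documents support only that it can, for one secondary outcome against one of two comparators. Comparator B excludes women with preventive claims (9.2.2.2), so it does not have this entry route.

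**What to change.** 1. In 9.6.2.5.3, add a sensitivity analysis for SGA versus A that limits A to women with a preventive claim before LMP, within the half-life window already set in 9.2.2.1. Describe separately the women who enter A only through a first fill in pregnancy on or after a new hypertension diagnosis.
2. Reconcile the wording on A in 9.2.2.1 with the before-or-during wording in 8.1 and the other statements of the objectives, so that it is clear whether first use in pregnancy qualifies.
3. In 9.6.2.4.1, state that L contains only pre-exposure baseline variables, so that pre-eclampsia and other pregnancy events listed in 9.3.3 are kept out of the weights.

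A claims-based start-time rule is preferable to a primary entry rule that asks whether the drug was plausibly for migraine, which would be too subjective to program reproducibly.

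The cost is protocol wording and one additional rule on claims already extracted. The downside is a smaller comparator A and lower precision in that sensitivity analysis; the main analysis population need not change.

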#### **9.2.2.2 Exclusion Criteria**

Women who are exposed to known teratogens (eg, valproate or topiramate) or other CGRP antagonists will be excluded if exposure to these substances occurs within five of their half-lives prior to LMP.

For comparator cohort B, women who have pharmacy claims for any preventive migraine medications will be excluded.

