**Exposure period and definition:**

*Erenumab-aooe exposed:* claims for erenumab-aooe in the 112 days prior to the index date or during the pregnancy period  
*Comparator Cohort:* no claims for erenumab-aooe in the 112 days prior to the LMP or during the pregnancy period

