### **9.6.2.5 Sensitivity Analysis**

#### **9.6.2.5.1 Subgroup Analysis**

Subgroups that will be explored if there is sufficient sample size include maternal age group at LMP (16-17 years, 18-40 years, 41-44 years), calendar year at LMP, comorbidities or medication use at baseline, concomitant medication use during pregnancy, dose of erenumab-aooe taken (70 or 140 mg), and patients who have migraine with aura or chronic migraine.

In addition to assessing outcomes in pregnant women exposed to erenumab-aooe before or during pregnancy and those not exposed to erenumab-aooe before or during pregnancy, we will also explore proportions of each of the outcomes in subgroups of the unexposed cohort, including migraine patients exposed to other CGRPs, migraine patients exposed to erenumab more than 112 days prior to the estimated date of conception and not during the pregnancy, migraine patients exposed to other preventive migraine medications, and migraine patients exposed to known teratogens in the one month prior to or during pregnancy. Also, outcomes will be described in migraine patients with claims for acute medication during the pregnancy.

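### The exclusion of known teratogens ends at the LMP, so first-trimester starters stay in the malformation analysis, mainly in comparator A

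*Protocol*

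**What the plan says.** Section 9.2.2.2 addresses "Women who are exposed to known teratogens (eg, valproate or topiramate) or other CGRP antagonists", who "will be excluded if exposure to these substances occurs within five of their half-lives prior to LMP". The window closes at the LMP.

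Cohort entry does not close there. For comparator A, section 9.2.2.1 states that "we will include women who are exposed to other preventive medications during pregnancy as well as before LMP". Section 9.3.1 likewise counts erenumab claims both before the LMP and during pregnancy as exposure.

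The named teratogens are themselves migraine preventives. Section 7.1 lists "anticonvulsants (eg, topiramate and divalproex sodium), and botulinum toxin" among the most commonly used preventive therapies, and later says that topiramate and valproic acid are to be avoided in pregnancy because they are teratogenic.

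Section 9.6.2.5.1 plans to explore, within the unexposed cohort, users of other CGRP drugs and "migraine patients exposed to known teratogens in the one month prior to or during pregnancy".

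Section 9.3.1 describes comparator A as women "who do not have pharmacy claims for erenumab-aooe in the 112 days prior to the LMP but do have evidence of the use" of other preventives, and comparator B as women who "do not have pharmacy claims for erenumab-aooe or other anti-CGRP medications 112 days prior to the LMP date or during pregnancy". The exposure definition under the Study Design Schema requires of comparators "no claims for erenumab-aooe in the 112 days prior to the LMP or during the pregnancy period".

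**The concern.** Malformations are the primary outcome, and erenumab against other preventives is the lead contrast in the abstract's comparative analyses. A woman whose first topiramate or valproate fill falls after the LMP but within the first trimester qualifies for A through that fill and meets no exclusion. If such women gather in A, its malformation risk rises above that of a non-teratogenic preventive group, and an increase with erenumab becomes harder to see. The study is sized for a doubling of risk, so modest contamination matters.

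Weighting is not a dependable remedy. Section 9.6.2.4.1 restricts the propensity model to baseline confounders, and section 9.2.4 sets baseline as the 365 days before the LMP. Section 9.3.3 does record suspected teratogens by trimester. But where the teratogen is the drug that places a woman in A, it is part of the comparator treatment and not a confounder that can be weighted away.

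**Working it through.** **Inputs from the protocol (sections 9.5 and 9.6):** background malformation prevalence p0 = 3%; target relative risk 2.0, so p1 = 6%; 1:4 matching; 80% power. Two-sided alpha of 0.05 is inferred from the 95% intervals. Table 2 gives 425 exposed live births for relative risk 2.00; 425 is used here as that column labels it.

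**Step 1: reproduce the plan's figure.** With pooled variance under the null and no continuity correction:

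n = [1.96·√(p̄(1−p̄)(1+1/4)) + 0.842·√(p1(1−p1) + p0(1−p0)/4)]² / (p1−p0)²

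p̄ = (0.06 + 4×0.03)/5 = 0.036, so n = (0.4082 + 0.2124)² / 0.03² = 428, against 425 stated. Power at 425 is 79.8%. The figure reproduces.

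**Step 2: add teratogen exposure to comparator A.** Let f be the share of A's infants exposed to a teratogen in the first trimester and r its relative risk. The documents give neither; both are assumptions. Here f counts only women still in A after section 9.2.2.2 has removed those with qualifying pre-LMP exposure.

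Comparator risk = 0.03 × [1 + f(r−1)]. Observed ratio = true ratio / [1 + f(r−1)].

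With a true relative risk of 2.0 and no teratogen use in the erenumab arm:

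| f | r | Risk in A | Observed RR | Power at 425 | Exposed infants needed |
|---|---|---|---|---|---|
| 0 | – | 3.00% | 2.00 | 79.8% | 428 |
| 5% | 2 | 3.15% | 1.90 | 75% | 486 |
| 5% | 3 | 3.30% | 1.82 | 70% | 553 |
| 10% | 2 | 3.30% | 1.82 | 70% | 553 |
| 10% | 3 | 3.60% | 1.67 | 60% | 730 |
| 20% | 2 | 3.60% | 1.67 | 60% | 730 |
| 20% | 3 | 4.20% | 1.43 | 37% | 1,403 |

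**Step 3: vary where the exposure sits.** The gap applies to every cohort.

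- Erenumab arm only, true ratio 1.0: the observed ratio is 1 + f(r−1), which runs from 1.05 (5%, r = 2) to 1.40 (20%, r = 3).
- Equal share in both arms, true ratio 2.0: if the effects multiply, the ratio stays at 2.00. If the teratogen adds the same absolute risk in each arm, the ratio is (0.06 + 0.03f(r−1)) / (0.03[1 + f(r−1)]), which runs from 1.95 (5%, r = 2) to 1.71 (20%, r = 3).

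**Step 4: compare the group definitions.**

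- *Comparator B.* Section 9.2.2.2 removes women with claims for any preventive, and section 9.3.1 bars other anti-CGRP drugs before the LMP and during pregnancy. Only teratogens that are not migraine preventives could remain.
- *Other CGRP drugs.* Section 9.2.2.2 excludes them before the LMP only; section 9.3.1 bars them from B in pregnancy as well; section 9.6.2.5.1 expects them in the unexposed cohort. The three do not agree.
- *Teratogens.* Section 9.6.2.5.1 looks at the month before pregnancy and at pregnancy itself; section 9.2.2.2 uses five half-lives before the LMP. The pre-LMP windows differ, and only the former reaches into pregnancy.
- *Comparator A and erenumab.* The A sentence in section 9.3.1 omits claims during pregnancy, which the Schema definition includes.

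**The case against.** The strongest case against is about size and direction. No passage supports any particular share or relative risk. Women with qualifying exposure before the LMP are already out, and section 7.1's own statement that these drugs should be avoided in pregnancy suggests few new starts, though it gives no figure. The gap is common to all cohorts, so masking is not the only possible result. There are partial safeguards: teratogens recorded by trimester, subgroups by concomitant medication in pregnancy, quantitative bias analysis, and replication against comparator B. All of this stands and limits how far the size can be pressed. None of it closes the gap in the eligibility rule.

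A reader might also infer several stronger points that the documents do not support:

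- *That the three groups overlap and the comparison is undefined.* Section 9.2.2.2, the objectives in section 8.1 and section 9.6.2.4.1 all keep preventive users out of B. The Schema definition, the first paragraph of section 9.3.1 and section 9.6.2.4.2 treat erenumab claims in pregnancy as exposure. The A and B sentences in section 9.3.1 are drafting omissions to be aligned.
- *That section 9.6.2.5.1 shows an intention to keep teratogen users in the formal comparison.* It plans only to explore proportions in subgroups of an unexposed cohort, does not name A or B, and itself conflicts with the eligibility rules.
- *That other CGRP drugs mask a signal.* This needs a malformation effect of those drugs, which the documents do not establish.

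**Conclusion.** The point holds for the erenumab versus comparator A malformation contrast. As written, the exclusion lets a woman who starts a known teratogen after the LMP remain, A's entry rule admits her, and baseline weights cannot be relied on to correct it. Concentration in A is the plausible case, because A is defined by preventive use and the named teratogens are preventives; it biases the ratio downwards.

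The size is illustrative: the range of 1.90 to 1.43 for a true relative risk of 2.0, with power of 75% to 37%, rests wholly on the assumed 5-20% share, the assumed relative risk of 2-3 and no teratogen use in the erenumab arm. With use in that arm the direction can reverse or the bias can largely cancel. The existence of the gap rests on the text alone. For other CGRP drugs, the finding is only that the sections disagree.

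**What to change.** For the malformation analysis, apply the teratogen exclusion in all cohorts from the existing pre-LMP window through the first trimester as section 9.3.1 defines it (LMP to day 90). At a minimum, make this a prespecified sensitivity analysis. The analysis is in live-born infants, so every pregnancy has passed day 90 and the longer window is observed equally in all of them; this would not be so for spontaneous abortion. Report the excluded women descriptively, outside the unexposed cohort of section 9.6.2.5.1.

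Reconcile sections 9.2.2.1, 9.2.2.2, 9.3.1 and 9.6.2.5.1 on exposure after the LMP to teratogens and to other CGRP drugs. Align section 9.3.1 with the Schema definition and section 9.2.2.2: A without erenumab claims in the 112 days before the LMP or during pregnancy, and B without claims for any preventive.

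The cost is protocol wording, code-list logic and the loss of some comparator A women. These are changes to analytic eligibility and do not touch treatment.
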